## 6.4. APPENDIX 4: CDC Working Case Definition of Pericarditis, Myocarditis, and Myopericarditis Occurring After Receipt of COVID-19 mRNA Vaccines

The CDC working case definition of pericarditis, myocarditis, and myopericarditis to be used in this study is presented in [Table 16](#).

**Table 16: CDC Working Case Definition of Pericarditis, Myocarditis, and Myopericarditis Occurring After Receipt of COVID-19 mRNA Vaccines**

Condition	Definition	
Acute myocarditis	Probable Case	Confirmed Case
	Presence of $\geq 1$ new or worsening of the following clinical symptoms a	Presence of $\geq 1$ new or worsening of the following clinical symptoms a
	
 
• Chest pain, pressure, or discomfort.
 
	
 
• Chest pain, pressure, or discomfort.
 

	
 
• Dyspnea, shortness of breath, or pain with breathing.
 
	
 
• Dyspnea, shortness of breath, or pain with breathing.
 

	
 
• Palpitations.
 
	
 
• Palpitations.
 

	
 
• Syncope.
 
	
 
• Syncope.
 

	OR , infants and children aged $< 12$ years might instead have $\geq 2$ of the following symptoms:	OR , infants and children aged $< 12$ years might instead have $\geq 2$ of the following symptoms:
	
 
• Irritability.
 
	
 
• Irritability.
 

	
 
• Vomiting.
 
	
 
• Vomiting.
 

	
 
• Poor feeding.
 
	
 
• Poor feeding.
 

	
 
• Pachypnea.
 
	
 
• Tachypnea.
 

	
 
• Lethargy.
 
	
 
• Lethargy.
 

	AND	AND
	$\geq 1$ new finding of	$\geq 1$ new finding of
	
 
• Troponin level above the upper limit of normal (any type of troponin).
 
	
 
• Histopathologic confirmation of myocarditisb.
 

	
 
• Abnormal ECG or rhythm monitoring findings consistent with myocarditisc.
 
	
	
 
• Abnormal cardiac function or wall motion abnormalities on an echocardiogram.
 
	
 
• cMRI findings consistent with myocarditis in the presence of a troponin level above the upper
 

Condition	Definition	
	
 
cMRI findings consistent with myocarditis.
 
	limit of normal (any type of troponin).
	AND	AND
	
 
No other identifiable cause of the symptoms and findings.
 
	
 
No other identifiable cause of the symptoms and findings.
 

Acute pericarditisd	Presence of $\geq 2$ new or worsening of the following clinical features:	
	
 
Acute chest pain.
 
	
	
 
Pericardial rub on examination.
 
	
	
 
New ST-elevation or PR-depression on ECG.
 
	
	
 
New or worsening pericardial effusion on echocardiogram or magnetic resonance imaging.
 
	
Myopericarditis	This term may be used for participants who meet the criteria for both myocarditis and pericarditis.	

Abbreviations: AV = atrioventricular; CEAC = Cardiac Event Adjudication Committee; cMRI = cardiac magnetic resonance imaging; ECG = electrocardiogram.

Note: An independent CEAC comprised of medically qualified personnel, including cardiologists, will review suspected cases of myocarditis, pericarditis, and myopericarditis to determine if they meet Center for Disease Control and Prevention criteria for “probable” or “confirmed” events, ([Gargano et al 2021](#)) and provide the assessment to the Sponsor. The CEAC members will be blinded to study treatment. Details regarding the CEAC composition, responsibilities, procedures, and frequency of data review will be defined in the CEAC charter.

- Persons who lack the listed symptoms but who meet other criteria may be classified as subclinical myocarditis (probable or confirmed).
- Using the Dallas criteria ([Aratz et al 1987](#)). Autopsy cases may be classified as confirmed clinical myocarditis on the basis of meeting histopathologic criteria if there is no other identifiable cause.
- To meet the ECG or rhythm monitoring criterion, a probable case must include at least one of 1) ST-segment or T-wave abnormalities; 2) Paroxysmal or sustained atrial, supraventricular, or ventricular arrhythmias; or 3) AV nodal conduction delays or intraventricular conduction defects.

Using either the original or the revised Lake Louise criteria.  
<https://www.sciencedirect.com/science/article/pii/S0735109718388430?via%3Dihubexternal icon>

- <https://academic.oup.com/eurheartj/article/36/42/2921/2293375external icon>
- Typically described as pain made worse by lying down, deep inspiration, or cough and relieved by sitting up or leaning forward, although other types of chest pain might occur.

[figure not shown]
Source: [Gargano et al 2021](#).

## 6.5. APPENDIX 5: Protocol Amendment History

### 6.5.1. Protocol Amendment 4

Amendment 4, 14 Feb 2023:

CCI

[figure not shown]
CCI

### **6.5.2. Protocol Amendment 3**

**Amendment 3, 17 June 2022:**

CCI

[figure not shown]
CCI

[figure not shown]
### **6.5.3. Protocol Amendment 2**

**Amendment 2, 10 May 2022:**

[figure not shown]
CCI

CCI

[figure not shown]
CCI

[figure not shown]

## DOCUMENT HISTORY

Version	Date	Description of major modifications
CCI		

## List of Abbreviations

Abbreviation	Definition
Ab	Antibody
AE	Adverse event
AESI	Adverse event of special interest
ANCOVA	Analysis of covariance
AR	Adverse reaction
ATC	Anatomical Therapeutic Chemical
bAb	binding antibody
BD	Booster dose
BMI	Body mass index
CDC	Center for Disease Control and Prevention
CEAC	Cardiac Event Adjudication Committee
CI	Confidence interval
COVID-19	Coronavirus Disease 2019
CRF	Case report form
CRO	Contract research organization
CSP	Clinical study protocol
CSR	Clinical study report
DBL	Database lock
DSMB	Data safety monitoring board
eCRF	electronic case report form
EDC	Electronic data capture
eDiary	electronic diary
EoS	End of study
FAS	Full analysis set
GLSM	Geometric least squares mean
GMFR	Geometric mean fold-rise
GM	Geometric mean
GMC	Geometric mean concentration
GMR	Geometric mean titer ratio
GMT	Geometric mean titer
HA	Hemagglutination
HAI	Hemagglutination inhibition
HCP	Healthcare practitioner
HLGT	High level group term
IA	Interim analysis
IcEv	Intercurrent event
IM	Intramuscular(ly)
IP	investigational product
IRT	Interactive Response Technology
LB	Lower bound
LLOQ	Lower limit of quantification

MAAE	Medically-attended adverse event
MedDRA	Medical Dictionary for Regulatory Activities
nAb	neutralizing antibody
PostBD	Post booster dose
PP	Per-protocol
PreBD	Prior to booster dose
PT	Preferred term
RSV	Respiratory Syncytial Virus
SAE	Serious adverse event
SAP	Statistical analysis plan
SAS	Statistical analysis system
SARS-CoV-2	Severe acute respiratory syndrome coronavirus 2
SCR	Seroconversion rate
SD	Standard deviation
SOC	System organ class
SMQ	Standardized MedDRA Queries
SRR	Seroresponse rate
Supportive PP Set	Supportive PP Set for Group 1 and Group 2 Comparison
TEAE	Treatment-emergent adverse event
TFLs	Tables, Figures, and Listings
ULOQ	Upper limit of quantification
WHO-DD	World Health Organization Drug Dictionary

## **1. Introduction**

This SAP is based on CSP (Amendment 5, dated on 16-June-2023) and approved eCRF (version 16.038, dated on 01-August-2023).

In addition to the information presented in the statistical consideration sections of the protocol (Sections 2.8, 3.8, and 4.8) which provides the principal features of analyses for this study, this SAP provides statistical analysis details/data derivations. It also documents modifications or additions to the analysis plan which are not “principal” in nature and result from information that was not available at the time of protocol finalization. If the methods in this SAP differ from the methods described in the protocol, the SAP will prevail.

Study mRNA-1345-P302 is a Phase 3, randomized, observer-blind, study to evaluate safety, tolerability, and immunogenicity of mRNA-1345, an mRNA vaccine targeting RSV, when given alone or coadministered with a seasonal influenza vaccine or SARS-CoV-2 vaccine and when given as an open-label boost at 1 Year following a primary dose in adults  $\geq$  50 years of age.

PPD Biostatistics and programming team, designee of Moderna Biostatistics and Programming department, will perform the statistical analysis. SAS Version 9.4 or higher will be used.

In this document, injection and dose are used interchangeably.

## **2. Part A**

### **2.1. Study Objectives**

#### **2.1.1. Primary Objectives**

##### **2.1.1.1. Primary Safety Objective**

The primary safety objective of the study is to evaluate the safety and tolerability of the mRNA-1345 vaccine coadministered with a seasonal influenza vaccine (Afluria Quadrivalent).

##### **2.1.1.2. Primary Immunogenicity Objective**

The primary immunogenicity objectives are:

- 1) To evaluate the impact of coadministered influenza vaccine on the immune response to RSV-A
- 2) To evaluate the impact of coadministered RSV vaccine on the immune response to influenza

#### **2.1.2. Secondary Objectives**

##### **2.1.2.1. Key Secondary Immunogenicity Objectives**

The key secondary immunogenicity objectives are:

- To evaluate the impact of coadministered influenza vaccine on the immune response to RSV-B
- To evaluate the impact of coadministered RSV vaccine on the immune response to influenza based on seroconversion from baseline

### **2.1.2.2. Other Secondary Immunogenicity Objectives**

The other secondary immunogenicity objectives are:

- To evaluate the Ab response to mRNA-1345 with and without a seasonal influenza vaccine (Afluria Quadrivalent)
- To evaluate the Ab response to seasonal influenza vaccine (Afluria Quadrivalent) with and without mRNA-1345

### **2.1.3. Exploratory Objectives**

The exploratory objectives, which may be performed, are as follows:

- To further characterize the immune response across study vaccines

## **2.2. Study Endpoints**

### **2.2.1. Primary Endpoints**

#### **2.2.1.1. Primary Safety Endpoints**

The primary safety objective will be evaluated by the following safety endpoints:

- Numbers and percentages of participants with solicited local and systemic ARs over the 7 days post-injection
- Numbers and percentages of participants with unsolicited AEs through 28 days post-injection
- Numbers and percentages of participants with MAAEs, SAEs, AESIs, and AEs leading to withdrawal from Day 1 (baseline) to Day 181/EoS

#### **2.2.1.2. Primary Immunogenicity Endpoints**

The primary immunogenicity objectives will be evaluated by the following coprimary endpoints:

- GMT of serum RSV-A nAbs at Day 29
- SRR in serum RSV-A nAbs at Day 29. Seroresponse for RSV-A nAbs is defined as a post-injection titer is  $\geq 4x$  LLOQ if baseline is  $<$  LLOQ, or a  $\geq 4$ -fold rise from baseline in post-baseline titer if baseline is  $\geq$  LLOQ.

- GMT of serum anti-HA Abs as measured by HAI assay for influenza A strains and B strains at Day 29

## 2.2.2. Secondary Endpoints

### 2.2.2.1. Key Secondary Immunogenicity Endpoints

The key secondary immunogenicity objectives will be evaluated by the following endpoints:

- GMT of serum RSV-B nAbs at Day 29
- SRR in serum RSV-B nAbs at Day 29. Seroresponse is defined in the same way as for RSV-A nAbs.
- SCR in seasonal influenza anti-HA Abs for influenza A and B strains at Day 29. Seroconversion for an influenza strain is defined as a post-injection titer  $\geq 1:40$  if baseline is  $< 1:10$ , or a  $\geq 4$ -fold rise from baseline in post-baseline titer if baseline is  $\geq 1:10$ .

### 2.2.2.2. Other Secondary Immunogenicity Endpoints

The other secondary immunogenicity objectives will be evaluated by the following endpoints:

- GMT and GMFR of post-injection/baseline titers to RSV-A nAbs up to Day 181/EoS
- GMT and GMFR of post-injection/baseline titers to RSV-B nAbs up to Day 181/EoS
- SRR and proportion of participants with  $\geq 2$ -fold increases in RSV-A nAb titers up to Day 181/EoS. A  $\geq z$ -fold increase in RSV A nAb titers is defined as a post-injection titer is  $\geq z \times \text{LLOQ}$  if baseline is  $< \text{LLOQ}$ , or a  $\geq z$ -fold increase from baseline in post-injection titers if baseline is  $\geq \text{LLOQ}$ .
- SRR and proportion of participants with  $\geq 2$ -fold increases in RSV-B nAb titers up to Day 181/EoS. A  $\geq z$ -fold increase in RSV-B nAb titers is defined in the same way as for RSV-A nAbs.
- SCR and proportion of participants with  $\geq 2$ -fold increases at Day 181/EoS in seasonal influenza anti-HA Abs measured by HAI assay. A  $\geq z$ -fold increase in anti-HA Ab titers is defined in the same way as for RSV-A nAbs.
- GMT and GMFR of post-injection/baseline titers to serum seasonal influenza anti-HA Abs as measured by HAI assay up to Day 181/EoS.

### 2.2.3. Exploratory Endpoints

- GMC and GMFR of post-injection/baseline concentration to RSV bAbs up to Day 181/EoS
- Proportions of participants with  $\geq$  2-fold and  $\geq$  4-fold increases in RSV bAb concentration up to Day 181/EoS. A  $\geq$  z-fold increase in RSV bAb concentration is defined in the same way as for RSV-A nAbs.
- Frequency, specificities, or other endpoints to be determined for the further characterization of immune responses.

## 2.3. Study Design

### 2.3.1. Overall Study Design

Part A is a Phase 3, randomized, observer-blind study to evaluate safety, tolerability, and immunogenicity of mRNA-1345, an mRNA vaccine targeting RSV, when given alone or coadministered with a seasonal influenza vaccine (Afluria Quadrivalent) in adults  $\geq$  50 years of age.

All participants will participate in a Screening period (up to 14 days before Day 1), treatment period (vaccine and/or placebo administration on Day 1 [Baseline]), and a follow-up period (up to 6 months after vaccination). The SoA is provided in [Appendix F](#).

The study will enroll approximately 1620 medically stable adults  $\geq$  50 years of age. On Day 1, each participant will receive 2 injections administered IM, one in each arm, in the deltoid muscle. Participants will be randomized as shown in [Table 1](#) to receive either 1) mRNA-1345 (█ μg) + placebo (0.9% sodium chloride [normal saline]); 2) mRNA-1345 (█ μg) + Afluria Quadrivalent; or 3) Afluria Quadrivalent + placebo. Randomization will be stratified by age (50 to 59 years, 60 to 74 years, and  $\geq$  75 years). The study will target enrollment of approximately 20% of participants 50 to 59 years of age.

**Table 1: Randomized Groups**

Group Name	Sample Size	Vaccine Administered
Group 1	420	mRNA-1345 (█ μg) + placebo in contralateral arms
Group 2	600	mRNA-1345 (█ μg) + Afluria Quadrivalent in contralateral arms
Group 3	600	Afluria Quadrivalent + placebo in contralateral arms

Participants will have a total of 8 visits/safety telephone calls. At the dosing visit on Day 1, participants will be instructed how to document and report solicited ARs in a provided eDiary. Solicited ARs will be assessed from Day 1 through Day 7 (the day of injection and the following 6 days), and local solicited ARs will be assessed separately for each injection site. Unsolicited AEs will be assessed from Day 1 through Day 28 (the day of injection and the following 27 days). SAEs, MAAEs, AEs leading to withdrawal, and AESIs will be assessed from Day 1 through Day 181/EoS.

Blood sample collection for humoral immunogenicity will occur on Day 1, Day 29, and Day 181/EoS. The samples will be processed and analyzed as per the Laboratory Manual. The Day 8 visit (Visit 2) may be either at the study site or a via a telephone call. The study site staff will perform scheduled safety telephone calls to participants on Day 57, Day 91, Day 121, and Day 151 to collect AEs, MAAEs, AESIs, AEs leading to withdrawal, SAEs, and information about concomitant medications related to those events and receipt of non-study vaccinations.

An IRT error in Part A conduct was identified in March 2023. More details are provided in [Section 2.3.4](#).

### **2.3.2. Statistical Hypothesis**

The immunogenicity primary objectives are to evaluate the effect of coadministered influenza vaccine on the immune response to RSV-A virus and influenza A and B strains included in Afluria Quadrivalent. There are 6 co-primary endpoints to support the primary objectives.

#### **Primary Objective to Evaluate the Impact on the Immune Response to RSV-A:**

##### Co-primary endpoints based on GMT at Day 29:

The null hypothesis  $H_0^1$ : immunogenicity response to mRNA-1345 in participants who received mRNA-1345 coadministered with Afluria Quadrivalent, as measured by GMT at Day 29 using RSV-A nAb assay, is inferior compared with that in participants who received mRNA-1345 plus placebo. The noninferiority in the GMT of RSV-A nAbs in participants who received mRNA-1345 coadministered with Afluria Quadrivalent compared with that in participants who received mRNA-1345 plus placebo will be demonstrated by the LB of the 95% CI of GMR of ruling out 0.667 (i.e., LB > 0.667), using noninferiority margin of 1.5. The GMR is the ratio of the GMT of RSV-A nAbs in participants who received mRNA-1345 coadministered with Afluria Quadrivalent compared with the GMT of RSV-A nAbs in participants who received mRNA-1345 plus placebo.

Co-primary endpoints based on Seroresponse Rate at Day 29:

The null hypothesis  $H_0^2$ : immunogenicity response to mRNA-1345 in participants who received mRNA-1345 coadministered with Afluria, as measured by SRR of RSV-A nAbs at Day 29, is inferior compared with that in participants who received mRNA-1345 plus placebo. The noninferiority in the SRR in participants who received mRNA-1345 coadministered with Afluria Quadrivalent compared with that in participants who received mRNA-1345 plus placebo will be demonstrated by the LB of the 95% CI of the SRR difference (coadministered group – mRNA-1345 plus placebo) of ruling out -10% (i.e., LB > -10%), using noninferiority margin of 10%.

**Primary Objective to Evaluate the Impact on the Immune Response to Influenza:**

Co-primary endpoints based on GMT at Day 29:

The null hypotheses  $H_0^3$  to  $H_0^6$ : immunogenicity response to Afluria Quadrivalent in participants who received Afluria Quadrivalent coadministered with mRNA-1345, as measured by GMT of anti-HA Abs for each of the 4 influenza strains at Day 29 using HAI assay, is inferior compared to that in participants who received Afluria Quadrivalent plus placebo. For each of the 4 influenza strains, the noninferiority in the GMT in participants who received mRNA-1345 coadministered with Afluria Quadrivalent compared with that in participants who received Afluria Quadrivalent plus placebo will be demonstrated by the LB of the 95% CI of the GMR of ruling out 0.667 (i.e., LB > 0.667), using noninferiority margin of 1.5. The GMR is the ratio of the GMT of anti-HA Abs in participants who received mRNA-1345 coadministered with Afluria Quadrivalent compared with the GMT of anti-HA Abs in participants who received Afluria Quadrivalent plus placebo.

**Key Secondary Objective to Evaluate the Impact on the Immune Response to RSV-B:**

Key secondary endpoint based on GMT at Day 29:

The null hypothesis  $H_0^7$ : immunogenicity response to mRNA-1345 in participants who received mRNA-1345 coadministered with Afluria Quadrivalent, as measured by GMT at Day 29 using RSV-B nAb assay, is inferior compared with that in participants who received mRNA-1345 plus placebo. The noninferiority in the GMT of RSV-B nAbs in participants who received mRNA-1345 coadministered with Afluria Quadrivalent compared with that in participants who received mRNA-1345 plus placebo will be demonstrated by the LB of the 95% CI of the GMR of ruling out 0.667 (i.e., LB > 0.667), using noninferiority margin of 1.5. The GMR is the ratio of the GMT of RSV-B nAbs in participants who received mRNA-1345 coadministered with Afluria compared with the GMT of RSV-B nAbs in participants who received mRNA-1345 plus placebo.

Hypothesis 7 will be assessed once all the primary hypotheses 1 to 6 are demonstrated.

**Key secondary endpoint based on SRR at Day 29:**

The null hypothesis  $H_0^8$ : immunogenicity response to mRNA-1345 in participants who received mRNA-1345 coadministered with Afluria Quadrivalent, as measured by SRR of RSV-B nAbs at Day 29, is inferior compared with that in participants who received mRNA-1345 plus placebo. The noninferiority in SRR of RSV-B nAbs in participants who received mRNA-1345 coadministered with Afluria Quadrivalent compared with that in participants who received mRNA-1345 plus placebo will be demonstrated by the LB of the 95% CI of the SRR difference (coadministered group – mRNA-1345 plus placebo) of ruling out -10% (i.e., LB > -10%), using noninferiority margin of 10%.

Hypothesis 8 will be assessed once all the primary hypotheses and the first key secondary hypothesis (i.e., hypothesis 1 to 7) are demonstrated.

**Key Secondary Objective to Evaluate the Impact on the Immune Response to Influenza Based on Seroconversion from Baseline:**

**Key secondary endpoint based on SCR at Day 29:**

The null hypotheses  $H_0^9$  to  $H_0^{12}$ : immunogenicity response to Afluria Quadrivalent in participants who received mRNA-1345 coadministered with Afluria Quadrivalent, as measured by SCR of anti-HA Abs for each influenza strain at Day 29 using HAI assay, is inferior compared with that in participants who received Afluria plus placebo. The noninferiority in SCR in participants who received mRNA-1345 coadministered with Afluria Quadrivalent compared with that in participants who received Afluria Quadrivalent plus placebo will be demonstrated by the LB of the 95% CI of the SCR difference (coadministered group – Afluria Quadrivalent plus placebo) of ruling out -10% (i.e., LB > -10%), using noninferiority margin of 10%.

Hypotheses 9 to 12 will be assessed once all the primary hypotheses and the key secondary hypotheses (i.e., hypothesis 1 to 8) are demonstrated.

The hierarchical order for the hypotheses to be tested is also indicated in [Figure 1](#)

### **2.3.3. Sample Size and Power**

The study will plan to randomize approximately 1620 participants, with approximately 420 participants receiving mRNA-1345 + placebo (Group 1), 600 participants receiving mRNA-1345 + Afluria Quadrivalent (Group 2), and 600 participants receiving Afluria Quadrivalent + placebo (Group 3).

With approximately 420 participants exposed to mRNA-1345 plus placebo, the study has approximately 95% probability to observe at least 1 participant with an AE at a true 0.7% AE rate. With approximately 600 participants exposed to mRNA-1345 plus Afluria Quadrivalent and Afluria Quadrivalent plus placebo, respectively, the study has approximately 95% probability to observe at least 1 participant with an AE at a true 0.5% AE rate.

**Sample Size and Power for the primary immunogenicity endpoints:**

Assuming approximately 10% of participants are ineligible to be included in the PP Set. The overall power considering meeting the primary objectives to evaluate the immune responses to RSV-A and influenza is 90%. Sample size justification for the co-primary immunogenicity endpoints is shown in [Table 2](#).

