The global power considering meeting the primary objectives to evaluate the immune responses to RSV-A and influenza is at least 90%. Sample size justification for the co-primary endpoints is shown in [Table 5](#).

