**Table 2: Sample Size Justification for the Co-primary Immunogenicity Endpoints**

Primary Endpoint	Number of Evaluable Participants (with 10% ineligible for Per-protocol Set)	$\alpha$	Standard Deviation	GMR/SRR Assumed	NI Margin	Power
mRNA-1345 Noninferiority (2-sided test)						
Day 29 GMT Coadministration (Group 2) vs. alone (Group 1)	378(Group 1) 540(Group 2)	0.05	1.5	GMR=1	1.5	98%
Day 29 SRR Coadministration (Group 2) vs. alone (Group 1)	378 (Group 1) 540 (Group 2)	0.05		SRR=0.8 in both groups	10%	96%
Afluria Quadrivalent Noninferiority (2-sided test) for Each Influenza Strain						
Day 29 GMT Coadministration (Group 2) vs. alone (Group 3)	540 (Group 2) 540 (Group 3)	0.05	1.5	GMR=1	1.5	99%
Overall power to show noninferiority of the primary immunogenicity endpoints						90%

With 540 participants to be included in PP Set in mRNA-1345 + Afluria Quadrivalent (Group 2) and 378 participants to be included in PP Set in mRNA-1345 + placebo (Group 1):

- There is at least 98% power to demonstrate the noninferiority of the immune response to RSV-A, as measured by GMT of RSV-A nAb in participants receiving mRNA-

1345 plus Afluria Quadrivalent compared with that in mRNA-1345 plus placebo group, at a 2-sided alpha of 0.05, assuming a noninferiority margin of 1.5 and an underlying GMR of 1. The standard deviation of the natural log-transformed level is assumed to be 1.5.

- There is at least 96% power to demonstrate the noninferiority of the immune response, as measured by SRR of RSV-A nAbs at Day 29 in participants receiving mRNA-1345 plus Afluria Quadrivalent compared with that in mRNA-1345 plus placebo group, at a 2-sided alpha of 0.05, assuming an SRR of RSV-A nAbs of 80% in both groups (a true SRR difference is 0), and a noninferiority margin of 10%.

With 540 participants to be included in PP Set in either mRNA-1345 plus Afluria Quadrivalent group (Group 2) or Afluria Quadrivalent plus placebo group (Group 3):

- There is at least 99% power to demonstrate noninferiority of the immune response to each of the 4 influenza strains, as measured by GMT of influenza anti-HA Abs for each strain in participants receiving mRNA-1345 plus Afluria Quadrivalent compared with that in Afluria Quadrivalent plus placebo group, at a 2-sided alpha of 0.05, assuming a noninferiority margin of 1.5 and an underlying GMR of 1. The standard deviation of the natural log-transformed level is assumed to be 1.5.

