#### **2.3.4. Randomization**

The randomization will be in a blinded manner using a centralized IRT, in accordance with pre-generated randomization schedules.

The study will enroll approximately 1620 medically stable adults  $\geq$  50 years of age. Participants will be randomized with a ratio of 7:10:10 to receive either 1) mRNA-1345 + placebo (Group 1, 420 participants); 2) mRNA-1345 + Afluria Quadrivalent (Group 2, 600 participants); or 3) Afluria Quadrivalent + placebo (Group 3, 600 participants). Randomization will be stratified by age (50 to 59 years, 60 to 74 years, and  $\geq$  75 years). The study will target enrollment of approximately 20% of participants 50 to 59 years of age. Randomization details is described in [Section 2.3.1](#).

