#### **An IRT error**

On 07-March-2023, the Sponsor was informed of an error in the randomization ratio in Part A. The IRT vendor inadvertently inactivated the enrollment for Group 1 when 959 participants were randomized in Part A as part of a system build to fix an unrelated issue on 25-May-2022. Group 1 remained inactive until 25-Jul-2022 while the enrollment of Part A was completed on 09- June-2022. As a result, approximately 250 participants, instead of protocol planned 420 participants, were randomized in Group 1. This IRT error caused an under enrollment of around 170 participants in Group 1 and an over enrollment in Group 2 and 3; and the actual ratio for participants randomized in the three Groups was approximately 5:14:14.

The above information was received after the EDC database of Part A was locked but before the selected Sponsor and CRO personal, as defined by the study Data Blinding Plan, are to be unblinded to perform the analyses, and before the immunogenicity data become available. The assessment of actual randomization ratio was also conducted in a blinded fashion.

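### Part A power is still stated for 420 participants in Group 1, although the SAP records that about 250 were randomized; overall power is about 83–87%, not 90%

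*SAP*

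**What the plan says.** SAP section 2.3.3 plans 420, 600 and 600 participants in Groups 1, 2 and 3. It continues "Assuming approximately 10% of participants are ineligible to be included in the PP Set" and so takes "378 participants to be included in PP Set in mRNA-1345 + placebo (Group 1"), with 540 evaluable in each of the other two groups. On that basis SAP Table 2 gives 98% power for RSV-A GMT, 96% for RSV-A seroresponse rate (SRR), 99% for each influenza strain and 90% overall. For all six endpoints together the text above the table states: "The overall power considering meeting the primary objectives to evaluate the immune responses to RSV-A and influenza is 90" (per cent). The bullets under the table are in the present tense, for example "There is at least 96% power to demonstrate the noninferiority of the immune response" for RSV-A SRR. The RSV-B key secondary endpoints carry the same 98% and 96%. The safety statement in 2.3.3 is "With approximately 420 participants exposed to mRNA-1345 plus placebo, the study has approximately 95% probability to observe at least 1 participant", where the assumed event rate is 0.7%. Protocol section 2.8.3 and Table 5 match: "The global power considering meeting the primary objectives to evaluate the immune responses to RSV-A and influenza is at least 90" (per cent).

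SAP section 2.3.4 first repeats the plan, "Participants will be randomized with a ratio of 7:10:10 to receive either 1) mRNA-1345 + placebo (Group 1, 420 participants"), and then describes the IRT error. Group 1 was inactivated once 959 participants had been randomized and stayed inactive until after Part A enrolment closed. As a result "approximately 250 participants, instead of protocol planned 420 participants, were randomized in Group 1", Groups 2 and 3 were over-enrolled, and the ratio became about 5:14:14. The sponsor learned of this on 7 March 2023. The SAP is based on protocol Amendment 5 (16 June 2023) and an eCRF dated 1 August 2023.

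**The concern.** Two adjacent sections of one SAP describe different trials. The power section uses an allocation that the randomization section says did not happen, and the SAP was written after the error was known. Sections 2.5.4.2.3 and Appendix I mention a power reduction, but the visible text nowhere gives its size.

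This matters because Part A succeeds only if all six co-primary endpoints pass (SAP 2.5.5). The loss falls entirely on the Group 2 versus Group 1 comparison, which carries two of the six. It also carries the RSV-B tests, which come next in the hierarchy and must pass before influenza seroconversion can be tested. If an RSV endpoint missed its margin, a reader would judge that miss against a stated 90% power that the recorded allocation does not support.

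**Working it through.** **Inputs from the SAP.** Two-sided alpha 0.05; GMT margin 1.5 with true GMR 1 and SD 1.5 on the natural-log scale; SRR 80% in both groups with a 10-point margin; 10% excluded from the Per-Protocol Set.

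**Achieved allocation.**
- Group 1 at the time of the error: 959 × 7/27 = 248.6, which agrees with about 250.
- Groups 2 and 3: 959 × 10/27 + (1620 − 959)/2 = 685.7 each. The rounded ratio gives 250 × 14/5 = 700.
- After 10% exclusion: about 225 against 617 (or 630).

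**Formulas.**
- GMT: SE = 1.5 × √(1/n₁ + 1/n₂); power from the noncentral t with noncentrality ln 1.5 / SE.
- SRR, normal approximation: SE = 0.4 × √(1/n₁ + 1/n₂); power = Φ(0.10/SE − 1.96). It was also calculated by enumerating the Miettinen-Nurminen test, which is the planned method.
- Overall: product of the six powers, treating the endpoints as independent.

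**Reproducing the plan (378/540/540).**
- GMT: SE = 0.1006; 0.4055/0.1006 = 4.03; power 98.1%.
- SRR: SE = 0.0268; 0.10/0.0268 = 3.73; power 96.1% (Miettinen-Nurminen 96.7%).
- Influenza: 99.3% per strain.
- Overall: 0.981 × 0.961 × 0.993⁴ ≈ 0.918. With the SAP's rounded figures, 0.98 × 0.96 × 0.99⁴ = 0.904.

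Every stated figure reproduces, so the method matches the plan's.

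**Achieved allocation (225/617/617).**
- GMT: SE = 0.1168; 0.4055/0.1168 = 3.47; power 93.4%.
- SRR: SE = 0.0312; 0.10/0.0312 = 3.21; power 89.4% (Miettinen-Nurminen 92.5%).
- Influenza: 99.7% per strain.
- Overall, independent: 0.934 × 0.894 × 0.997⁴ ≈ 0.83. With Miettinen-Nurminen for SRR it is about 0.855.
- Overall, with correlation between RSV-A GMT and SRR simulated: about 0.87 (0.927 for the planned design).

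| Quantity | Stated | Planned, recomputed | Achieved allocation |
|---|---|---|---|
| RSV-A GMT | 98% | 98.1% | 93.4% |
| RSV-A SRR, normal / Miettinen-Nurminen | 96% | 96.1% / 96.7% | 89.4% / 92.5% |
| Influenza GMT, per strain | 99% | 99.3% | 99.7% |
| All six | 90% | 92–93% | 83–87% |
| At least one AE at 0.7%, Group 1 | 95% | 94.8% | 82.7% |

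The AE row is 1 − 0.993⁴²⁰ = 0.948 and 1 − 0.993²⁵⁰ = 0.827. The rate that 250 participants would reveal with 95% probability is 1 − 0.05^(1/250) = 1.2%.

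**Sensitivity.** Using 630 for Groups 2 and 3, or 221/618 from a strict 5:14:14 split of 1620, moves each result by about a point or less. The RSV-B powers use the same inputs and fall by the same amounts.

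**The case against.** The strongest reply is that nothing was miscalculated. Section 2.3.3 is a sample-size justification, worded conditionally and tied to what the study will plan to randomize. As a record of the design it is correct. That stands: the fault is a missing reconciliation, not a slip in arithmetic.

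It is also true that the SAP is open about the event. It gives the cause, dates and numbers. It says the allocation was assessed blinded, before immunogenicity data were available. It adds a Supportive PP Set that pools about 180 participants from study mRNA-1345-P301 with Group 1. On the same assumptions that comparison (about 405 against 617) has 98.8% GMT power and 97.4% SRR power. However, it is supportive only and its added reference participants were not randomized against Group 2. The primary analysis stays on the Per-Protocol Set, which contains no P301 participants, so the pooling does not restore the power of the confirmatory test.

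On size, 83% is the least favourable reading, because it combines the normal SRR formula with independence. The planned test gives 85.5% under independence, and allowing for correlation gives about 87%. With no exclusions at all (250/685), overall power would be about 88% by the normal formula and about 90% by Miettinen-Nurminen. The shortfall therefore depends partly on the 10% exclusion, but that is the SAP's own assumption.

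Finally, enrolment has closed, so no sample-size decision can follow, and a failed result would be read mainly from its confidence interval. This limits the consequence but does not make the stated power right. The amendment summary and the SAP history are redacted, so the absence of a recalculation can be asserted only for the visible text.

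**Conclusion.** The point holds. SAP 2.3.3 and Table 2 state powers that the allocation recorded in 2.3.4 does not deliver. RSV-A GMT power is about 93% rather than at least 98%. RSV-A SRR power is about 89–92.5% rather than at least 96%. Overall power is about 83–87% rather than 90%. On the independence calculation that reproduces the plan, the chance of missing at least one co-primary endpoint roughly doubles, from 8% to 17%. The Group 1 AE-detection probability is 83% rather than 95%.

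These results assume about 225 and 617 evaluable participants, SD 1.5, SRR 80% and no true difference. Strong positive correlation among the endpoints would raise the overall figure, but it cannot exceed the weakest component (92.5% by Miettinen-Nurminen, 89.4% by the normal formula). Influenza power is slightly higher than planned. Type I error, margins, tests and the success rule are unaffected. The shortfall is moderate and disclosed but unquantified, and it should be corrected before the results are interpreted.

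**What to change.** In SAP 2.3.3 and Table 2, keep the 420/600/600 figures and label both the numbers and the powers as planned. Beside them give the achieved-allocation figures:
- about 225 against 617 evaluable for the RSV comparison;
- RSV-A GMT about 93% and SRR about 89–92%;
- overall about 83–87%, with the method and correlation assumption stated;
- 83% probability of at least one AE at a 0.7% rate in Group 1.

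Restate the RSV-B GMT and SRR powers in the same way, and cross-refer to 2.3.4. Say plainly that the pooled P301 analysis is supportive and does not alter the power of the confirmatory test. Protocol section 2.8.3 and Table 5 can carry the same note if the protocol is amended for another reason.

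The cost is wording, and stated powers that look less favourable. No participants, tests, margins or analysis sets change.
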